- Type of the reaction by reporting a diagnosis or if not available, symptoms
- Date and time to onset of the reaction
- End date of the reaction (will be reported in a follow-up report if the reaction is still ongoing at the time of first notification)
- Name of the drug related to the examination or procedure in cause, date and time of administration, dose administered
- Causal relationship to the drug related to the examination or procedure in cause (mandatory)
- Outcome (no recovery/ recovery / recovery with sequelae/ unknown/death).

Event leading to a SAE report should be reported in the AE section of the case report form.

SAEs should be followed up by the Physician until complete recovery of the patient or, if not possible, until stabilisation of sequelae. The Physician may be requested by the Sponsor to provide follow-up information in order to comply with current regulations as well as for comprehensive assessment purposes.

If a serious event occurs, the Physician is responsible for the measures to be taken to ensure the safety of the study participants.

In addition, if occurring after the end of the patient's follow-up period, SAEs that the Physician thinks may be associated with the study medication/procedure must be reported to the local Sponsor (local pharmacovigilance contact) regardless of the time between the event and the end of the study.

According to local requirements, the Sponsor will communicate relevant safety information to the appropriate agency(ies), International Review Board / Independent Ethics Committee and/or all active investigators, as it becomes available.

The transmission of the information to the Sponsor does not release the Physician from his/her responsibility to inform the regulatory authorities, if applicable.

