**12. Appendices**

Appendix 1: Form related to site characteristics and radiological activities

Appendix 2: Patient general questionnaire

Appendix 3: Patient FUP questionnaire.

Appendix 4: Suspect Adverse Reaction Report (F006031)

Appendix 5: Patient Information Sheet

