2.3. Safety criteria

Safety variables collected for this study are:

- Modalities of DOTAREM® administration
 - Volume injected,
 - Type of injection,
 - Number of injections,
 - Nature of package
- From DOTAREM® administration until end of usual follow up in the MR unit
 - Adverse events,
 - Serious adverse events,
 - Adverse events requiring the administration of a concomitant drug,
 - Adverse events according to intensity and outcome,
 - Adverse events related to contrast media injection.
- During the follow-up period

CONFIDENTIAL	FORM STATISTICAL ANALYSIS PLAN N° DGD-55-003 VERSION N° 2 DATED: 26 FEBRUARY 2018 (REF I011622)	F015830-01 Page 9 / 49
--------------	--	---------------------------

- Suspicion of NSF and final diagnosis of NSF,
- Medical events,
- Serum creatinine measurements.

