3.5. Handling of dropouts or missing data

If the start date of an adverse event is missing, then the adverse event occurs after the DOTAREM® injection.

No replacement of missing data is planned in this study.

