5.6.3. Adverse Events

Adverse events (AEs) will be coded in system organ classes and preferred terms using MedDRA dictionary v16.0.

Adverse events occurring or worsening after the "Treatment start date" (Date of MRI examination with DOTAREM®) will be considered as **treatment-emergent** adverse events (TEAEs).

An adverse event will be considered **related to** DOTAREM®, if the relationship to the study drug is doubtful, possible, not assessable or missing.

All AEs will be summarized in an incidence table and a specific table will focus on incidence of TEAEs.

Incidence tables will present the number and percent of patients reporting TEAEs, the number and percent of patients reporting serious adverse events (SAEs) and the number and percent of patients reporting related AEs by system organ class and preferred term.

Adverse event listings will be presented in CSR appendix 16.2.7.

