Table 14.3.3.4 Treatment Emergent Adverse Events by Primary System Organ Class and Preferred Term - Safety Population

Same as table 14.3.3.3

Table 14.3.3.5 Serious Treatment Emergent Adverse Events by Primary System Organ Class and Preferred Term - Safety Population

CONFIDENTIAL	FORM STATISTICAL ANALYSIS PLAN N° DGD-55-003 VERSION N° 2 DATED: 26 FEBRUARY 2018 (REF I011622)	F015830-01 Page 38 / 49
--------------	---	----------------------------

Same as table 14.3.3.3

Table 14.3.3.6 Treatment Emergent Adverse Events with Relationship to DOTAREM® by Primary System Organ Class and Preferred Term - Safety Population

Same as table 14.3.3.3

Table 14.3.3.7 Listing of Deaths - Safety Population

Patient Number	Primary System Organ Class Preferred Term Description	Start Date & Time/ Outcome	Seriousness/ Relationship to DOTAREM®	Intensity / Relationship to DOTAREM®	Administration of Concomitant Drug	Date of MRI Examination
xxxx	xxxxxxxxxxxxxxxxxxxxxx	mm/dd/yyyy hh:mm/	Death/ mm/dd/yyyy hh:mm	xxxxxxxxxxxxxx/	xxxxxxxxxxxxxx/	mm/dd/yyyy hh:mm
	xxxxxxxxxxxxxxxxxxxxxx	mm/dd/yyyy hh:mm	Life-threatening	xxxxxxxxxxxxxx	Yes/No/	
	xxxxxxxxxxxxxxxxxxxxxx	xxxx			Yes/No	

Etc.

MRI: Magnetic Resonance Imaging.

MedDRA dictionary version 16.0.

Source: Listing 16.2.7.1.

Table 14.3.3.8 Listing of Serious Adverse Events - Safety Population

Same as table 14.3.3.7

Table 14.3.4.1 Renal Status during Follow-up Period - Safety Population

		Follow-up 1 (N=XXX)	Follow-up 2 (N=XXX)	Follow-up 3 (N=XXX)
Serum Creatinine (Raw Data)	n	xxx	xxx	xxx
	Mean (SD)	xx.xx (xx.xx)	xx.xx (xx.xx)	xx.xx (xx.xx)
	Median	xx.x	xx.x	xx.x
	Min ; Max	xx.x ; xx.x	xx.x ; xx.x	xx.x ; xx.x
	Missing (if applicable)	xx	xx	xx
Serum Creatinine (Change from Baseline)	n	xxx	xxx	xxx
	Mean (SD)	xx.xx (xx.xx)	xx.xx (xx.xx)	xx.xx (xx.xx)
	Median	xx.x	xx.x	xx.x
	Min ; Max	xx.x ; xx.x	xx.x ; xx.x	xx.x ; xx.x
	Missing (if applicable)	xx	xx	xx

SD: Standard Deviation.

Source: Listing 16.2.8.1.

CONFIDENTIAL	FORM STATISTICAL ANALYSIS PLAN N° DGD-55-003 VERSION N° 2 DATED: 26 FEBRUARY 2018 (REF I011622)	F015830-01 Page 39 / 49
--------------	---	----------------------------

Table 14.3.5.1 Medical Events except MRI Examination during Follow-up Period - Safety Population

		Follow-up 1 (N=XXX)	Follow-up 2 (N=XXX)	Follow-up 3 (N=XXX)
Surgery	n	xxx	xxx	xxx
	Yes	xxx (xx.x%)	xxx (xx.x%)	xxx (xx.x%)
	No	xxx (xx.x%)	xxx (xx.x%)	xxx (xx.x%)
	Missing (if applicable)	xx	xx	xx
Pro-Inflammatory Syndrom	n	xxx	xxx	xxx

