Listing 16.2.7.1 Adverse Events - All Included Population

Patient #	Population Flag	Primary System Organ Class Preferred Term Nature of the Event	Start Date	Seriousness/ Outcome	Intensity / Relationship to DOTAREM®	Administration of Concomitant Drug	Date of MRI Examination with DOTAREM®
xxxx		xxxxxxxxxxxxxxxxxxxxxx	mm/dd/yyyy	Yes:Death/ not yet recovered	Moderate/Not related	Yes :xxxxxx	mm/dd/yyyy
		xxxxxxxxxxxxxxxxxxxxxx	mm/dd/yyyy	No/recovered	Mild/unknown	No	

Etc.

AIP: All Included Population ; EP: Efficacy Population ; SP: Safety Population ; MRI: Magnetic Resonance Imaging.
MedDRA dictionary version 16.0.

Listing 16.2.8.1 Renal Status during Follow-up Period - All Included Population

Patient #	Population Flag	Date of MRI Examination with DOTAREM®	Follow-up Visit	Date of Last Renal Function Assessment	Serum Creatinine (umol/L)	Serum Creatinine (Entered)	Unit

AIP: All Included Population ; EP: Efficacy Population ; SP: Safety Population ; MRI: Magnetic Resonance Imaging.

Listing 16.2.9.1 Nephrogenic Systemic Fibrosis Suspicion/Diagnosis - All Included Population

Patient #	Population Flag	Date of MRI Examination with DOTAREM®	NSF Suspicion	Source of Suspicion	Confirmatory Biopsy	Specify if No	Date of the Biopsy	Final Diagnosis of NSF	Specify if No

CONFIDENTIAL	FORM STATISTICAL ANALYSIS PLAN N° DGD-55-003 VERSION N° 2 DATED: 26 FEBRUARY 2018 (REF I011622)	F015830-01 Page 47 / 49
--------------	---	----------------------------

AIP: All Included Population ; EP: Efficacy Population ; SP: Safety Population ; MRI: Magnetic Resonance Imaging ; NSF: Nephrogenic Systemic Fibrosis.

Listing 16.2.9.2 Medical Events during Follow-up Period except MRI examination - All Included Population

Patient #	Population Flag	Date of MRI Examination with DOTAREM®	Follow-up Visit	Date of FU Visit	Medical Event Category	Medical Event Date	Primary System Organ Class (Preferred Term) [Description]	Medical Event Specify

AIP: All Included Population ; EP: Efficacy Population ; SP: Safety Population ; MRI: Magnetic Resonance Imaging ; FU: Follow-Up.
MedDRA dictionary version 16.0.

Listing 16.2.9.3 MRI examination during Follow-up Period - All Included Population

Patient #	Population Flag	Follow-up Visit	Date of FU Visit	Product ATC Name	Product Class	Product Name	Volume Administered (mL)	Date

AIP: All Included Population ; EP: Efficacy Population ; SP: Safety Population ; ATC: Anatomical Therapeutic Chemical ; FU: Follow-Up.
WHO DD dictionary version 2015.

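### The SAP's closed list for related adverse events omits 'unknown', a relationship value in its own listing shell, and would omit any grade above 'possible' if the form has one

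*SAP*

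**What the plan says.** SAP 5.6.3 classifies an adverse event as related to DOTAREM "if the relationship to the study drug is doubtful, possible, not assessable or missing". It names four values and gives no wording for stronger grades or for any other value.

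The same section promises "the number and percent of patients reporting related AEs by system organ class and preferred term". The output is Table 14.3.3.6, "Treatment Emergent Adverse Events with Relationship to DOTAREM® by Primary System Organ Class and Preferred Term - Safety Population". SAP 2.3 lists "Adverse events related to contrast media injection" among the safety variables, so this is a planned result.

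Actual relationship values are displayed in one other place, the shell for Listing 16.2.7.1 in SAP 7.3. Its column for intensity and relationship has two example entries. One reads "Moderate/Not related"; the other pairs mild intensity with 'unknown'.

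On missing data, SAP 3.5 says "No replacement of missing data is planned in this study". Protocol section 4 makes causality a mandatory item in a serious adverse event report but lists no grades. The report form and the patient questionnaires appear in the protocol text only as appendix titles.

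**The concern.** The rule is evidently meant to be cautious, since it counts doubtful, unassessable and even absent ratings as related. A cautious rule is safest when it names what is excluded and counts everything else. This one does the reverse, so any value its authors did not foresee becomes 'not related' by default.

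One such value appears in the SAP's own listing shell. Others would exist if the form grades causality above 'possible'. In either case a programmer who follows the sentence as written would leave those events out of Table 14.3.3.6, and no other summary table would show the omission.

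**Working it through.** The plan gives no figure to reproduce, so the check applies the rule literally to each relationship value and compares the result with the listing shell.

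**Step 1. Is 'unknown' a relationship value in the shell?** Listing 16.2.7.1 puts seriousness and outcome in one column and intensity and relationship in the next. The row with 'unknown' already shows a recovered outcome in the earlier column. The word therefore stands in the relationship position. It is not the 'Unknown' outcome category of Table 14.3.3.1.

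**Step 2. Does anything map it?** SAP 5.6.3 has no recoding rule. SAP 3.5 plans no replacement of missing data, and its only specific rule concerns a missing start date. No section equates 'unknown' with 'not assessable' or 'missing'.

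**Step 3. Apply the rule.**

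| Relationship value | Where it appears | SAP 5.6.3, read literally | Related unless recorded as not related |
|---|---|---|---|
| Doubtful | 5.6.3 | related | related |
| Possible | 5.6.3 | related | related |
| Not assessable | 5.6.3 | related | related |
| Missing | 5.6.3 | related | related |
| Not related | Listing 16.2.7.1 shell | not related | not related |
| Unknown | Listing 16.2.7.1 shell | **not related** | related |
| Any grade above 'possible' | not shown in either document | **not related**, if it exists | related |

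The two rules differ only in the last two rows. The sixth rests on the SAP alone. The seventh depends on a scale that the documents do not show.

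**Step 4. Which outputs depend on the rule?** The overall safety summary (Table 14.3.3.1) has rows for seriousness, intensity, outcome and concomitant drug but none for relationship, and Table 14.3.3.2 uses the same shell. Table 14.3.3.4 covers all treatment-emergent events; Tables 14.3.3.5 and 14.3.3.8 cover serious ones. None of these filters on relationship. Table 14.3.3.6 alone does. Listing 16.2.7.1 prints the recorded relationship for every event.

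**Step 5. Size.** Let k be the number of safety-population patients who have at least one treatment-emergent event recorded as unknown or above 'possible', and no treatment-emergent event that the present rule counts as related. With N patients in the safety population, the top line of Table 14.3.3.6 is understated by k patients, or 100 × k / N percentage points. Neither k nor N is given. SAP 3.3 and 4 say that 1,000 patients were not reached, so each such patient is worth more than 100 × 1 / 1,000 = 0.1 percentage point. That is visible in a table reported to one decimal place. If k = 0, this line does not change.

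**The case against.** The strongest reply is that the four values may be every option on the form other than 'not related'. No higher grade appears as a relationship value in either document. The SAP is dated February 2018, almost three years after recruitment stopped in March 2015, and its authors had seen data: they describe an uncorrectable creatinine value and withdrawn patients recorded as followed up. They may have written the list from the values on file, in which case the rule already does what the fix does. This inference is plausible but cannot be confirmed from the documents.

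The second reply is that 'unknown' is example text in a dummy shell. The shell is not a codelist: it shows neither 'doubtful' nor 'possible', and the word may be loose usage for 'not assessable' or 'missing', both of which count as related. That may be so, but the SAP does not say it. What remains is a mismatch of terms between rule and shell, with a definite consequence under a literal reading.

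A reader might go further and infer that the rule removes the events most likely caused by DOTAREM. The documents do not support this, because they do not show that a grade above 'possible' exists. A reader might also size the loss from the 0.4% adverse event rate in the protocol's background section. That is the rate of all adverse events in a different post-marketing study, not of related events in renally impaired patients, and the number finally enrolled here is not stated. Nor would any event leave the adverse event data as a whole.

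**Conclusion.** The point holds as a gap in the classification rule. For 'unknown' it rests only on the SAP: the shell uses the value, the rule omits it, and no section maps it. For grades above 'possible' it is conditional on a form that the documents do not reproduce.

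The effect is confined to Table 14.3.3.6. Affected events remain in the overall treatment-emergent table and the patient listing, and in the serious-event outputs if serious. The NSF endpoint does not use the rule, and no statistical test depends on it. The number of events misclassified is unknown and may be zero. The change is still worth making, because related events are a named safety criterion with a single summary table, and the fix costs almost nothing.

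**What to change.** Replace the sentence in SAP 5.6.3 with: *An AE is considered related to DOTAREM unless the relationship is recorded as not related.* State that unknown, not assessable and missing ratings, and any grade stronger than possible, therefore count as related. Use the same relationship terms in the Listing 16.2.7.1 shell, and preferably give the form's full causality scale beside the rule.

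The cost is one sentence and an aligned shell, with no new data collection. All four values now counted stay counted, so the number of related events can rise or stay the same but cannot fall. If no affected values were recorded, Table 14.3.3.6 is unchanged.

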5.6.4. Deaths, serious adverse events and other significant adverse events

All deaths and all SAEs experienced during the study will be separately listed sorted by patient number, presenting: , emergence, diagnosis or nature, system organ class (SOC), preferred term (PT), start date, the intensity, the relationship to study drug, the outcome, the action taken and the seriousness criteria.

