1.1. Study objectives

The primary objective of this study is to prospectively estimate the incidence of NSF in patients with moderate to severe renal impairment after administration of DOTAREM®. Patients will be followed during a two-year period after administration of DOTAREM®, to assess if signs or symptoms suggestive of NSF have appeared.

The secondary objectives of the study are:

- to collect a large number of data concerning the general safety profile of DOTAREM® during patient inclusion and MR examination,
- to collect information regarding MRI indication,
- to collect conditions of use/administration of the product in this specific population of patients,
- to collect efficacy data (image and diagnostic quality).

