7.1. Clinical study report in-text tables, figures and listings

7.2. Contents of clinical study report section 14

Table 14.1.1.1 Patient Overall Disposition - All Included Population

	Total (N=XXX)
Number of Patients not Prematurely Withdrawn	xxx (xx.x%)
Number of Patients Prematurely Withdrawn	xxx (xx.x%)
Reason of Withdrawal	
Retraction of Patient Consent	xxx (xx.x%)
Adverse Event	xxx (xx.x%)
Patient Lost to Follow-up	xxx (xx.x%)
Technical Incident	xxx (xx.x%)
Death	xxx (xx.x%)
Medical Decision	xxx (xx.x%)
Other	xxx (xx.x%)

#: (n row / N included) * 100.

Source: Listing 16.2.1.2.

Table 14.1.1.2 Disposition by Visit - All Included Population

	General Questionnaire (N=XXX)	Follow-up 1 (N=XXX)	Follow-up 2 (N=XXX)	Follow-up 3 (N=XXX)	At Least One Follow- up Visit
Number of Patients	xxx (xx.x%)	xxx (xx.x%)	xxx (xx.x%)	xxx (xx.x%)	xxx (xx.x%)

#: (n row / N included) * 100.

Source: Listing 16.2.1.1.

Table 14.1.1.3 Disposition by Site - All Included Population

	Total (N=XXX)
Argentina	Site 29 xxx (xx.x%)
	Site 30 xxx (xx.x%)
	Site 31 xxx (xx.x%)
Belgium	Site 1 xxx (xx.x%)

CONFIDENTIAL	FORM STATISTICAL ANALYSIS PLAN N° DGD-55-003 VERSION N° 2 DATED: 26 FEBRUARY 2018 (REF I011622)	F015830-01 Page 25 / 49
--------------	---	----------------------------

Total (N=XXX)		
	Site 2	xxx (xx.x%)
	Site 28	xxx (xx.x%)
Brazil	Site 3	xxx (xx.x%)
Columbia	Site 32	xxx (xx.x%)
	Site 33	xxx (xx.x%)
	Site 34	xxx (xx.x%)
France	Site 6	xxx (xx.x%)
	Site 26	xxx (xx.x%)
Germany	Site 8	xxx (xx.x%)
	Site 27	xxx (xx.x%)
India	Site 10	xxx (xx.x%)
Italy	Site 12	xxx (xx.x%)
	Site 13	xxx (xx.x%)
	Site 14	xxx (xx.x%)
Korea	Site 15	xxx (xx.x%)
	Site 16	xxx (xx.x%)
	Site 17	xxx (xx.x%)
	Site 18	xxx (xx.x%)
Spain	Site 19	xxx (xx.x%)
	Site 20	xxx (xx.x%)
	Site 35	xxx (xx.x%)
Turkey	Site 23	xxx (xx.x%)
	Site 37	xxx (xx.x%)
United Kingdom	Site 24	xxx (xx.x%)
	Site 25	xxx (xx.x%)
Uruguay	Site 36	xxx (xx.x%)
United States of America	Site 38	xxx (xx.x%)
	Site 39	xxx (xx.x%)

CONFIDENTIAL	FORM STATISTICAL ANALYSIS PLAN N° DGD-55-003 VERSION N° 2 DATED: 26 FEBRUARY 2018 (REF I011622)	F015830-01 Page 26 / 49
--------------	---	----------------------------

Total (N=XXX)	
Site 40	xxx (xx.x%)
Site 41	xxx (xx.x%)

#: (n row / N included) * 100.

Source: Listing 16.2.1.1.

Table 14.1.1.4 Centre Characteristics and Radiological Activities - All Centres

	n	Total (N=XX)
Type of Centre	n	xx
Private		xx (xx.x%)
Public		xx (xx.x%)
Other		xx (xx.x%)
Missing (if applicable)		xx

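### The SAP promises a listing of all deaths during the study but sources it only from adverse event records, so follow-up deaths recorded only as a withdrawal reason would be absent from it.

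*SAP*

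**What the plan says.** SAP section 5.6.4 commits to this: "All deaths and all SAEs experienced during the study will be separately listed sorted by patient number". The output is "Table 14.3.3.7 Listing of Deaths - Safety Population". Its shell in SAP section 7.2 is made of adverse event fields (MedDRA terms, start date, outcome, seriousness, relationship, intensity, concomitant drug) plus the MRI date, and the line beneath it reads "Source: Listing 16.2.7.1". That source is defined in section 7.3 as "Listing 16.2.7.1 Adverse Events - All Included Population". Table 14.3.3.1, which has a death row among its seriousness categories, cites the same source.

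SAP section 2.3 sets out when each kind of safety data is collected. Adverse events and SAEs stand under the heading "From DOTAREM® administration until end of usual follow up in the MR unit". A separate heading for the follow-up period begins with "Suspicion of NSF and final diagnosis of NSF" and adds only medical events and serum creatinine.

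Death also appears in disposition. In Table 14.1.1.1 it is one category under "Reason of Withdrawal", separate from the category for adverse events, and the table's source is the premature withdrawal listing, 16.2.1.2.

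**The concern.** The promise covers the whole study, and the study follows each patient for two years. The stated source covers adverse event records, which the SAP says are collected only while the patient is in the MR unit. A reader of the safety section would take Table 14.3.3.7 as complete, because section 5.6.4 says it is. The disposition table could then show more deaths than the death listing, with no planned step to explain the difference.

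This matters in a renally impaired cohort. Death ends the period in which NSF could be observed, so when patients died after DOTAREM is useful background to the NSF result. No other planned output supplies the detail: SAP section 6.2.3.5 marks death narratives as not applicable.

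**Working it through.** The plan gives no figure to reproduce and no arithmetic applies. The check follows a death from the form it is recorded on to the output it reaches.

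1. **Promise.** SAP 5.6.4: all deaths during the study. Under SAP 1.1 and 1.2 and protocol section 3.3, patients are followed for two years after administration.
2. **Output and source.** Table 14.3.3.7 takes its rows from Listing 16.2.7.1 and names no other source.
3. **What feeds that source.** Under SAP 2.3, adverse events and SAEs up to the end of MR-unit follow-up. SAP 1.2 gives a similar scope. Table 14.1.1.4 groups the centres' usual post-examination follow-up as under 30 minutes, 30 minutes to 1 hour, or over 1 hour. The last category is open-ended, but the scale is plainly not two years.
4. **What is collected afterwards.** NSF suspicion and diagnosis, medical events and serum creatinine. Protocol section 4 gives adverse event and SAE notification to the radiologist. The follow-up physician's explicit prompt-reporting duty over the two years is for NSF.
5. **Where a later death can be recorded.** On the withdrawal form, with death as the reason. This reaches Table 14.1.1.1 and Listing 16.2.1.2, whose columns are date of withdrawal, withdrawal status, who decided and the reason. There is no cause, coded term or relationship to the product.
6. **Whether either follow-up listing feeds the death listing.** Listing 16.2.1.2 is not a source of Table 14.3.3.7. Neither is Listing 16.2.9.2 (follow-up medical events), which has no outcome or seriousness column and so could not identify a fatal event reliably.

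The resulting paths are:

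| How the death is recorded | Disposition (14.1.1.1, 16.2.1.2) | Death listing (14.3.3.7) |
|---|---|---|
| As an adverse event with death as seriousness criterion | only if also entered as a withdrawal | yes |
| As withdrawal reason only | yes | no |
| As both | yes | yes, with no planned reconciliation |

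The second row is the gap.

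**The case against.** The strongest reply is that the protocol is wider than SAP 2.3. Its sections 3.3 and 4 refer to usual follow-up after administration and do not confine it to the MR unit. Death is one of the SAE criteria, and any event that triggers an SAE report is also to be entered in the adverse event section of the case report form. SAEs are followed to recovery or stabilisation. NSF suspicion at any time in the two years goes on the same reaction report. Protocol section 4 also asks, as an addition, for SAEs thought to be related that occur after a patient's follow-up has ended; that is easier to understand if SAEs within follow-up are already reportable. Listing 16.2.7.1 itself has no time filter. All of this stands: some later deaths can reach the death listing. A reader might infer that every death in follow-up will be missing, but the documents do not support that. They are ambiguous on late SAEs.

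A reader might also infer that these deaths vanish from the report. They do not. Table 14.1.1.1 counts them and Listing 16.2.1.2 gives patient, date and reason. The MRI date in Listing 16.2.1.1 allows an approximate interval to be worked out by hand. Nor would a difference between the tables necessarily be a contradiction: Table 14.1.1.1 counts withdrawal reasons in all included patients, while Table 14.3.3.7 covers adverse events in the Safety Population.

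Finally, SAP 1.1 limits the general safety objective: "to collect a large number of data concerning the general safety profile of DOTAREM® during patient inclusion and MR examination". A death listing based on adverse events fits that objective. It does not fit the wording of section 5.6.4, which is not limited in this way. The death row of Table 14.3.3.1 is a seriousness category and does not claim to count all deaths; it needs a label, not a correction.

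**Conclusion.** The mismatch is real and limited. Followed as written, the SAP gives a death listing that omits any death recorded only as a reason for withdrawal, under a section that promises all of them. The defect lies in completeness and traceability of a safety output. It does not change the NSF proportions in SAP 5.6.2, because the death listing feeds no denominator there.

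The number affected cannot be stated. The documents give no mortality rate, say only that 1000 patients were not reached, and do not fix the length of MR-unit follow-up. A reader might multiply an assumed cohort size by an assumed mortality rate, or compare an hour with two years, and infer that nearly all deaths would be absent. None of those inputs is in the documents, and the reporting routes in protocol section 4 make the share that reaches the adverse event section unknown.

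The conclusion rests on two readings: that the source line under Table 14.3.3.7 is complete, and that withdrawal deaths are not routinely entered as adverse events as well. If every such death was also entered as an SAE, the listing would be complete in practice, but the plan contains no step to confirm it.

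**What to change.** - Build Table 14.3.3.7, for the Safety Population, from Listing 16.2.7.1 (seriousness criterion death) together with Listing 16.2.1.2 (withdrawal reason death). Cite both as sources.
- Reconcile the two by patient number, so that a death recorded in both appears once, and mark the source of each row.
- Show days from DOTAREM administration to death. Where no death date is recorded, show days to the withdrawal date and label it as such, since Listing 16.2.1.2 gives a withdrawal date and not a date of death.
- In Table 14.3.3.1, label the death row as deaths reported as adverse events, and add a row or cross-reference for deaths recorded as withdrawals.

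Follow-up medical events should not be relied on as a third source, because Listing 16.2.9.2 has no field that identifies a fatal outcome.

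The cost is SAP wording and one merge of two listings that are already planned. The listing becomes longer, and cause and relationship will be blank for deaths known only from the withdrawal form. If the merge is not done, the minimum is to restrict section 5.6.4 to deaths reported as adverse events and refer the reader to Listing 16.2.1.2 for the others.
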